## PROTOCOL SUMMARY OF CHANGES

Page no.	Changes in Protocol Amendment 1 [26 February 2020] (New information is marked in red)	Page no.	Protocol V1.0 [06 November 2019] (Removed/updated information is marked in blue)
24/108	
Key Secondary Objective:
 
Efficacy
 
To assess the effect of clobetasol propionate ophthalmic nanoemulsion 0.05% on eye pain associated with cataract surgery after one week of treatment
 
Other secondary objectives
 
Efficacy
 
[...]
 
-To assess the effect of clobetasol propionate ophthalmic nanoemulsion 0.05% on eye pain and on eye discomfort associated with cataract surgery
	4/90	
Secondary Objectives:
 
Efficacy
 
[...]
 
- To assess the effect of clobetasol propionate ophthalmic nanoemulsion 0.05% on eye pain/discomfort associated with cataract surgery

28/108	
Exclusion Criteria:
 
20) Presence of IOP <math>\geq</math>24 mmHg in the study eye at Visit 1
	8/90	
Exclusion Criteria:
 
20) Presence of IOP <math>\geq</math>24 mmHg at Visit 1


Study Evaluations:
 
Visit-1 (Screening; Day <math>-7 \pm 3</math> days): [...]
 
 
- Eye pain evaluation (VAS)
 
- Eye discomfort evaluation
 
 
[...]
 
Visit 1 (Baseline; Day 1, 24h after the surgery): [...]
 
 
- Eye pain evaluation (VAS)
 
- Eye discomfort evaluation
 
 
[...]
 
Visit 2 (Day <math>3 + 1</math> day): - Eye pain evaluation (VAS)
 
 
- Eye discomfort evaluation
 
 
[...]
 
Visit 3 (Day <math>8 \pm 1</math> day): - Eye pain evaluation (VAS)
 
 
- Eye discomfort evaluation
 
 
[...]
 
Visit 4 (Day <math>15 \pm 2</math> day): - Eye pain evaluation (VAS)
 
 
- Eye discomfort evaluation
 
 
[...]
 
Visit 5 (Day <math>29 \pm 2</math> day): - Eye pain evaluation (VAS)
 
 
- Eye discomfort evaluation
 
 
[...]
	28/108	
Study Evaluations:
 
Visit-1 (Screening; Day <math>-7 \pm 3</math> days): [...]
 
 
- Eye pain/discomfort evaluation (VAS)
 
 
[...]
 
Visit 1 (Baseline; Day 1, 24h after the surgery): [...]
 
 
- Eye pain/discomfort evaluation (VAS)
 
 
[...]
 
Visit 2 (Day <math>3 + 1</math> day): - Eye pain/discomfort evaluation (VAS)
 
[...]
 
Visit 3 (Day <math>8 \pm 1</math> day): - Eye pain/discomfort evaluation (VAS)
 
[...]
 
Visit 4 (Day <math>15 \pm 2</math> day): - Eye pain/discomfort evaluation (VAS)
 
[...]
 
Visit 5 (Day <math>29 \pm 2</math> day): - Eye pain/discomfort evaluation (VAS)
 
[...]
	8/90
--	--------	--	------

32/108	
Key secondary endpoint:
 
 
• Proportion of patients with VAS pain of “0” (no eye pain) compared to placebo at Day 8
 
 
Secondary endpoints:
 
Efficacy
 
[...]
 
 
• Change from Baseline to Day 3, Day 8, Day 15 and Day 29 compared to placebo in the VAS pain score
 
• Proportion of patients with VAS pain of “0” compared to placebo at Day 3, Day 15 and Day 29
 
• Change from Baseline to Day 3, Day 8, Day 15 and Day 29 compared to placebo in the proportion of patients with different discomfort grades
 
• Proportion of patients with no discomfort (“None”) compared to placebo at Day 3, Day 8, Day 15 and Day 29
 
• Change over time in the VAS pain score reported in the patients’ diaries compared to placebo
 
	12/90	
Secondary endpoints:
 
Efficacy
 
[...]
 
 
• Change from Baseline to Day 3, Day 8, Day 15 and Day 29 compared to placebo in the VAS pain/discomfort score
 
• Proportion of patients with VAS pain/discomfort of “0” compared to placebo at Day 3, Day 8, Day 15 and Day 29
 
• Change over time in the VAS pain/discomfort score reported in the patients’ diaries compared to placebo
 

--------	---	-------	---

34/108	
Key Secondary Analysis:
 
The aim of the key secondary analysis of this study is to assess the superiority of clobetasol propionate ophthalmic nanoemulsion 0.05% compared to placebo with respect to the key secondary endpoint in the FAS.
 
The key secondary analysis will be based on a single study eye for each patient. Each patient's study eye will be defined as the surgery eye.
 
The test will be the proportion of study eyes with no pain (VAS pain = 0) at Visit 3 (Day 8 ± 1 day) without receiving rescue medication as compared between clobetasol propionate ophthalmic nanoemulsion 0.05% dosed QID and placebo dosed QID using the chi square statistic.
 
The PP population set will be also tested to confirm the robustness of the key secondary analysis.
	n/a	
There is no previous information about Key Secondary Analysis in protocol version final 1.0 06 November 2019.

49/108	
Secondary Objectives
 
a) Key secondary objective
 
Efficacy
 
- To assess the effect of clobetasol propionate ophthalmic nanoemulsion 0.05% on eye pain associated with cataract surgery after one week of treatment.
 
b) Other secondary objectives
 
Efficacy
 
[...]
 
- To assess the effect of clobetasol propionate ophthalmic nanoemulsion 0.05% on eye pain and on eye discomfort associated with cataract surgery.
	30/90	
Secondary Objectives
 
Efficacy
 
[...]
 
- To assess the effect of clobetasol propionate ophthalmic nanoemulsion 0.05% on eye pain/discomfort associated with cataract surgery.
 
[...]

[figure not shown]
[figure not shown]
50/108	
4.1 Overview
 
If a patient wants to discontinue from the study, he/she will be treated according to the clinical practice. Patients who discontinue the study treatment, will be requested to continue attending their remaining study visits. If the patient does not accept, and wants to discontinue from the study, they will be encouraged to at least attend the Early Termination Visit (Section 4.3.2.8) as soon as possible.
	31/90	
4.1 Overview
 
If a patient wants to discontinue from the study, he/she will be treated according to the clinical practice. Patients who discontinue the treatment will complete the assessments planned for Early Termination Visit (Section 4.3.2.8) as soon as possible.

51/108	
Figure 1 Diagram of Study Design
  
* Patients who, for any reason, withdraw from the study treatment will be highly encouraged to continue attending all their remaining study visits to collect the most complete efficacy and safety data.
	32/90	
Figure 2 Diagram of Study Design
 

Table 1 Schedule of Observations										Table 1 Schedule of Observations									
Visit number	Visit -1 Screening	Cataract Surgery	Visit 1 Baseline	Visit 2	Visit 3	Visit 4	Visit 5	Early termination	Visit number	Visit -1 Screening	Cataract Surgery	Visit 1 Baseline	Visit 2	Visit 3	Visit 4	Visit 5	Early termination		
52/108	Day -7 (± 3 days)	Day -4	Day 1	Day 3 (± 1 day)	Day 6 (± 1 day)	Day 15 (± 2 days)	Day 29 (± 2 days)		33/90	Day -7 (± 3 days)	Day -1	Day 1	Day 3 (± 1 day)	Day 6 (± 1 day)	Day 15 (± 2 days)	Day 29 (± 2 days)			
	[...]									[...]									
	Eye pain (VAS) *	X		X	X	X	X	X		Eye pain/discomfort (VAS) *	X		X	X	X	X	X	X	
	Eye discomfort*	X		X	X	X	X	X		End of study / early termination documentation						X	X		
	[...]									[...]									
	4. VAS scales and discomfort should be assessed prior to any physical evaluation									4. VAS scales should be assessed prior to any physical evaluation									
	[...]									[...]									

From 54 to 56/108	
4.3.2.1 Visit -1 (Screening visit at Day <math>-7 \pm 3</math> days)
 
[...]
 
 
- Eye pain (VAS) – to be assessed prior to any physical evaluation
 
- Eye discomfort – to be assessed prior to any physical evaluation
 
 
[...]
 
4.3.2.2 Visit 1 (Baseline visit at Day 1, 24 h after the cataract surgery)
 
[...]
 
 
- Eye pain (VAS) – to be assessed prior to any physical evaluation
 
- Eye discomfort – to be assessed prior to any physical evaluation
 
 
[...]
 
After IMP administration:
 
 
- Distribution of patient diary:           
 
o Throughout the study, patients or caregivers should record on it: doses and schedule of IMP administration, eye pain VAS scores and cataract surgery-associated symptoms.
 
 
 
 
[...]
 
4.3.2.3 Visit 2 (Day 3 + 1 day)
 
[...]
 
 
- Eye pain (VAS) – to be assessed prior to any physical evaluation
 
- Eye discomfort – to be assessed prior to any physical evaluation
 
 
[...]
	
4.3.2.1 Visit -1 (Screening visit at Day <math>-7 \pm 3</math> days)
 
[...]
 
 
- Eye pain/discomfort (VAS) – to be assessed prior to any physical evaluation
 
 
[...]
 
4.3.2.2 Visit 1 (Baseline visit at Day 1, 24 h after the cataract surgery)
 
[...]
 
 
- Eye pain/discomfort (VAS) – to be assessed prior to any physical evaluation
 
 
[...]
 
After IMP administration:
 
 
- Distribution of patient diary:           
 
o Throughout the study, patients or caregivers should record on it: doses and schedule of IMP administration, eye pain/discomfort and photophobia VAS scores and cataract surgery-associated symptoms.
 
 
 
 
[...]
 
4.3.2.3 Visit 2 (Day 3 + 1 day)
 
[...]
 
 
- Eye pain/discomfort (VAS) – to be assessed prior to any physical evaluation
 
 
4.3.2.4 Visit 3 (Day <math>8 \pm 1</math> day)
 
[...]
 
 
- Eye pain/discomfort (VAS) – to be assessed prior to any physical evaluation
 
 
[...]


[figure not shown]

4.3.2.4 Visit 3 (Day 8 ± 1 day)
 
[...]
 
- Eye pain (VAS) – to be assessed prior to any physical evaluation
 
- Eye discomfort – to be assessed prior to any physical evaluation
 
[...]
 
4.3.2.5 Visit 4 (Day 15 ± 2 days)
 
[...]
 
- Eye pain (VAS) – to be assessed prior to any physical evaluation
 
- Eye discomfort – to be assessed prior to any physical evaluation
 
[...]
 
4.3.2.6 Visit 5 (Day 29 ± 2 days)
 
[...]
 
- Eye pain (VAS) – to be assessed prior to any physical evaluation
 
- Eye discomfort – to be assessed prior to any physical evaluation
 
[...]
 
4.3.2.8 Early Termination Visit
 
At any time, the investigator will make every attempt to ensure that an Early Termination Visit will be held, in the case of patient discontinuing the study (see Section 5.3).
 
At the Early Termination Visit, the following activities and assessments will be performed (NOTE: All ocular assessments must be performed in both eyes):
 
- Eye pain (VAS) – to be assessed prior to any physical evaluation
 
- Eye discomfort – to be assessed prior to any physical evaluation
	
4.3.2.5 Visit 4 (Day 15 ± 2 days)
 
[...]
 
- Eye pain/discomfort (VAS) – to be assessed prior to any physical evaluation
 
[...]
 
4.3.2.6 Visit 5 (Day 29 ± 2 days)
 
[...]
 
- Eye pain/discomfort (VAS) – to be assessed prior to any physical evaluation
 
[...]
 
4.3.2.8 Early Termination Visit (anytime during the 14 days Treatment period)
 
In case of early treatment discontinuation or withdrawal of the study during the 14-days treatment period (Section 5.3), every attempt will be made to ensure an Early Termination Visit will be held.
 
At Early Termination Visit, the following activities and assessments will be performed (NOTE: All ocular assessments must be performed in both eyes):
 
- Eye pain/discomfort (VAS) – to be assessed prior to any physical evaluation
 
[...]

---	---

	[...]		
61/108	5.2 Exclusion Criteria 20) Presence of IOP $\geq 24$ mmHg in the study eye at Visit 1	42/90	5.2 Exclusion Criteria 20) Presence of IOP $\geq 24$ mmHg at Visit 1


5.3 Withdrawal, Premature Discontinuation of Study Medication, and Replacement of Patients
 
Patients are free to discontinue their participation in the study at any time. Additionally, patients may be withdrawn from study at any time, if deemed necessary by the investigator (after discussion with the Medical Monitor). Withdrawal from the study will not affect or prejudice the patients' further care or treatment.
 
Potential reasons for withdrawal of patients from this study are:
 
 
• The decision of a patient to withdraw informed consent
 
• Patient is lost to follow-up (Section 5.3.1)
 
 
Potential reasons for premature discontinuation of study medication include, but are not limited to:
 
 
• Occurrence of a treatment-emergent AE (TEAE) or considerable worsening of an AE that, in the opinion of the investigator in consultation with the Medical Monitor and Sponsor, represents an unacceptable risk to the patient if he/she continues to receive study medication. The investigator must follow the patient until the AE resolves or satisfactorily stabilizes
 
• Administration of a rescue medication. Any patient placed on rescue therapy will discontinue the use of the IMP (see Sections 6.7.1 and 6.7.2)
 
• Patient's failure to comply with protocol requirements or study related procedures
 
• In case of pregnancy. The investigator will continue the follow-up of the patient until the end of the pregnancy
 
• Any surgery (different from the actual routine cataract surgery on the study eye) in the study or contralateral eye
 
 
In any case of premature discontinuation of study medication, the investigator must make extensive efforts to ensure that the patient will attend all his/her remaining study visits until study completion
	
5.3 Withdrawal, Premature Discontinuation of Study Medication, and Replacement of Patients
 
Patients are free to discontinue their participation in the study at any time. Withdrawal from the study will not affect or prejudice the patients' further care or treatment. Additionally, patients may be withdrawn from study at any time, if deemed necessary by the investigator.
 
Potential reasons for withdrawal of patients from this study are:
 
 
• The decision of a patient to withdraw informed consent
 
• Investigator withdrawal of the patient (after discussion with Medical Monitor)
 
• Occurrence of a treatment-emergent AE (TEAE) or considerable worsening of an AE that, in the opinion of the investigator in consultation with the Medical Monitor and Sponsor, represents an unacceptable risk to the patient if he/she continues to receive study medication. The investigator must follow the patient until the AE resolves or satisfactorily stabilizes
 
• Patient is lost to follow-up (Section 5.3.1)
 
• Administration of a rescue medication. Any patient placed on rescue therapy will discontinue use of the IMP and continue his/her study participation through Visit 5 (Sections 6.7 and 6.7.2)
 
• Patient's failure to comply with protocol requirements or study related procedures
 
• Pregnancy
 
• Any surgery (different from the actual routine cataract surgery on the study eye) in the study or contralateral eye
 
 
[...]

---	--

	(at Visit 5), aiming to collect the most complete efficacy and safety data. [...]		
68/108	
6.7.2 Rescue Medication
 
Any patients not responding adequately to the IMP may be rescued and placed on alternate therapy (Section 6.7) at the investigator's discretion at any time.
 
The choice of rescue medication is at the investigator's discretion. Any patient placed on rescue therapy will discontinue the use of the IMP and the investigator must make extensive efforts to ensure that the patient will attend all his/her remaining study visits, until study completion, aiming to collect the most complete efficacy and safety data.
 
Additionally, patients will be asked to phone the study center at any time to speak to a member of the medical personnel should they experience any worsening of ocular conditions or other AEs.
 
[...]
	51/90	
6.7.2 Rescue Medication
 
Any patients not responding adequately to the IMP may be rescued and placed on alternate therapy (Section 6.7) at the investigator's discretion at any time.
 
The choice of rescue medication is at the investigator's discretion. Any patient placed on rescue therapy will discontinue use of the IMP and continue his/her study participation through Visit 5.
 
Patients will be asked to phone the study center at any time to speak to a member of the medical personnel should they experience any worsening of ocular conditions or other AEs.
 
[...]

69/108	
7.1 Primary Efficacy Endpoint
 
Proportion of patients with anterior chamber cell grade of "0" (absence of cells) compared to placebo at Day 8.
 
Anterior chamber cell grade will be assessed by the investigator during slit-lamp examination and will be graded on an adapted 6-point scale proposed by the Standardization of Uveitis Nomenclature (SUN) working group (23) (Table 2)
	
7.1 Primary Efficacy Endpoint
 
Proportion of patients with anterior chamber cell grade of "0" (absence of cells) compared to placebo at Day 8.
																											
	
Table 2 Grading scheme for anterior chamber cells
 
  
 Grade	Cells in field†	
   
 0	0	
 
 0.5+	1-5	
 
 1+	6-15	
 
 2+	16-25	
 
 3+	26-50	
 
 4+	>50	
  
 
†Feld size is a 1 mm by 1 mm slit beam
	Grade	Cells in field †	0	0	0.5+	1-5	1+	6-15	2+	16-25	3+	26-50	4+	>50	
7.2 Primary efficacy assessment
 
Anterior chamber cell grade will be assessed by the investigator during slit-lamp examination and will be graded on a 6-point scale proposed by the Standardization of Uveitis Nomenclature (SUN) working group (23) (Table 2)
 
Table 2 The SUN working group grading scheme for anterior chamber cells
 
  
 Grade	Cells in field†	
   
 0	<1	
 
 0.5+	1-5	
 
 1+	6-15	
 
 2+	16-25	
 
 3+	26-50	
 
 4+	>50	
  
 
†Feld size is a 1 mm by 1 mm slit beam
	Grade	Cells in field †	0	<1	0.5+	1-5	1+	6-15	2+	16-25	3+	26-50	4+
Grade	Cells in field †																												
0	0																												
0.5+	1-5																												
1+	6-15																												
2+	16-25																												
3+	26-50																												
4+	>50																												
Grade	Cells in field †																												
0	<1																												
0.5+	1-5																												
1+	6-15																												
2+	16-25																												
3+	26-50																												
4+	>50																												

69/108	
7.2 Key Secondary Efficacy Endpoint
 
Proportion of patients with VAS pain of "0" (no eye pain) compared to placebo at Day 8.
 
Eye pain score will be assessed by the patient before any ocular examination and will be scored by ticking on a continuous scale comprised of a 10 cm (100 mm) horizontal line anchored by two verbal descriptions: "no eye pain" (score of 0) and "worst imaginable eye pain" (score of 10).
 	n/a	There is no previous information about Key Secondary Efficacy Endpoint in the protocol version final 1.0 06 November 2019.
--------	---	-----	---

[figure not shown]
71/108	
7.3 Other Secondary Efficacy Endpoints
 
Other secondary efficacy endpoints will be:
 
[...]
 
 
• Change from Baseline to Day 3, Day 8, Day 15 and Day 29 compared to placebo in the VAS pain score
 
• Proportion of patients with VAS pain of "0" compared to placebo at Day 3, Day 15 and Day 29
 
• Change from Baseline to Day 3, Day 8, Day 15 and Day 29 compared to placebo in the proportion of patients with different discomfort grades
 
• Proportion of patients with no discomfort ("None") compared to placebo at Day 3, Day 8, Day 15 and Day 29
 
• Change over time in the VAS pain score reported in the patients' diaries compared to placebo
 
	53/90	
7.3 Secondary Efficacy Endpoints
 
The secondary efficacy endpoints will be:
 
[...]
 
 
• Change from Baseline to Day 3, Day 8, Day 15 and Day 29 compared to placebo in the VAS pain/discomfort score
 
• Proportion of patients with VAS pain/discomfort of "0" compared to placebo at Day 3, Day 8, Day 15 and Day 29
 
• Change over time in the VAS pain/discomfort score reported in the patients' diaries compared to placebo
 

--------	---	-------	---

71/108	
7.3.1 Secondary efficacy assessments
 
[...]
 
 
The eye pain VAS is a single-item continuous scale comprised of a 10 cm (100 mm) horizontal line anchored by two verbal descriptors, one for each symptom extreme. For eye pain intensity, the scale is anchored by “no eye pain” (VAS score of 0) and “worst imaginable eye pain” (score of 100 mm)
 
 
The eye pain VAS is completed by the patient. Details and instructions for use of eye pain VAS can be found in Appendix 4
 
 
The eye discomfort will be assessed by using the categorical scale which can be found in Appendix 5
 
 
 
The photophobia VAS is a single-item continuous scale comprised of a 10 cm (100 mm) horizontal line anchored by two verbal descriptors, one for each symptom extreme. For photophobia intensity, the scale is anchored by “no photophobia” (score of 0) and “worst imaginable photophobia” (score of 100 mm)
 
 
The photophobia VAS is completed by the patient. Details and instructions for use of photophobia VAS can be found in Appendix 6
	54/90	
7.3.1 Secondary efficacy assessments
 
[...]
 
 
The eye pain/discomfort VAS is a single-item continuous scale comprised of a 10 cm (100 mm) horizontal/vertical line anchored by two verbal descriptors, one for each symptom extreme. For eye pain/discomfort intensity, the scale is anchored by “no eye pain/discomfort” (score of 0) and “worst imaginable eye pain/discomfort” (score of 100 mm)
 
 
The eye pain/discomfort VAS is completed by the patient. Details and instructions for use of eye pain/discomfort VAS can be found in Appendix 4
 
 
The photophobia VAS is a single-item continuous scale comprised of a 10 cm (100 mm) horizontal/vertical line anchored by two verbal descriptors, one for each symptom extreme. For photophobia intensity, the scale is anchored by “no photophobia” (score of 0) and “worst imaginable photophobia” (score of 100 mm)
 
 
The photophobia VAS is completed by the patient. Details and instructions for use of photophobia VAS can be found in Appendix 5

72/108	
7.5.2 Medical History
 
A detailed medical history of relevant conditions and procedures will be obtained by the investigator or qualified designee at the Screening visit (Visit –1) and recorded as required in the Medical History section of the eCRF.
 
[...]
	55/90	
7.5.2 Medical History
 
A detailed medical history of relevant conditions and procedures will be obtained by the investigator or qualified designee at the Baseline visit (Visit –1) and recorded as required in the Medical History section of the eCRF.
 
[...]

75/108	
8.2 Appropriateness of Measurements
 
Standardized methods for measurements of efficacy and safety variables will be used. The investigator assessment instruments and Patient-Reported Outcomes (eye pain and photophobia VAS and discomfort categorical scale) are accepted standards for clinical evaluation.
	57/90	
8.2 Appropriateness of Measurements
 
Standardized methods for measurements of efficacy and safety variables will be used. The investigator assessment instruments and Patient-Reported Outcomes (eye pain/discomfort and photophobia VAS) are accepted standards for clinical evaluation.

80/108	
8.3.8 SAE Reporting Contact Details
 
All SAEs should be faxed or sent by e-mail to [REDACTED] within 24 hours of the investigator becoming aware of the event(s). If the SAE Report Form Clinical Trials is faxed, the "Fax cover sheet, SAE report" should be used.
 
[REDACTED]    Fax: [REDACTED]    E-mail: [REDACTED]
	63/90	
8.3.8 SAE Reporting Contact Details
 
All SAEs should be faxed or sent by e-mail to [REDACTED] within 24 hours of the investigator becoming aware of the event(s). If the SAE Report Form Clinical Trials is faxed, the "Fax cover sheet, SAE report" should be used.
 
[REDACTED]    Fax: [REDACTED]    Phone: [REDACTED]    E-mail: [REDACTED]

85/108	
9.1.10 Primary Analysis
 
[...]
 
The PP population set will be also tested to confirm the robustness of the primary analysis.
 
The primary estimand (efficacy estimand) will be defined as the effect of the randomized treatments in all subjects meeting selection criteria assuming continuation of randomized treatments for the duration of the study regardless of actual compliance.
	67/90	
9.1.10 Primary Analysis
 
[...]
 
The PP population set will be also tested to confirm the robustness of the primary analysis.

85/108	
9.1.11 Key Secondary Analysis
 
The aim of the key secondary analysis of this study is to assess the superiority of clobetasol propionate ophthalmic nanoemulsion 0.05% compared to placebo with respect to the key secondary endpoint in the FAS.
 
The key secondary analysis will be based on a single study eye for each patient. Each patient's study eye will be defined as the surgery eye.
 
The test will be the proportion of study eyes with no pain (pain = 0) at Visit 3 (Day 8 ± 1 day) without receiving rescue medication as compared between clobetasol propionate ophthalmic nanoemulsion 0.05% dosed QID and placebo dosed QID using the chi square statistic.
 
The PP population set will be also tested to confirm the robustness of the key secondary analysis.
	n/a	There is no previous information about Key Secondary Analysis in the protocol version final 1.0 06 November 2019.
86/108	
9.1.14 Sensitivity Analysis
 
Sensitivity analysis will be carried out for possible intercurrent events such as discontinuation due to AE, lack of efficacy and use of rescue / prohibited medication. New estimands associated to each intercurrent event will be added to the already existing primary estimand accordingly.
	n/a	There is no previous information about Key Secondary Analysis in the protocol version final 1.0 06 November 2019.

102/108	13.2 Appendix 2														
	Slit Lamp Examination														
	[...]														
	- Anterior Chamber Cells														
	
  
 Grade	Cells in field	
   
 0	0	
 
 0.5+	1-5	
 
 1+	6-15	
 
 2+	16-25	
 
 3+	26-50	
 
 4+	>50	
  
	Grade	Cells in field	0	0	0.5+	1-5	1+	6-15	2+	16-25	3+	26-50	4+	>50
Grade	Cells in field														
0	0														
0.5+	1-5														
1+	6-15														
2+	16-25														
3+	26-50														
4+	>50														
[...]															
85/90	13.2 Appendix 2														
	Slit Lamp Examination														
	[...]														
	- Anterior Chamber Cells														
	
  
 Grade	Cells in field	
   
 0	<1	
 
 0.5+	1-5	
 
 1+	6-15	
 
 2+	16-25	
 
 3+	26-50	
 
 4+	>50	
  
	Grade	Cells in field	0	<1	0.5+	1-5	1+	6-15	2+	16-25	3+	26-50	4+	>50
Grade	Cells in field														
0	<1														
0.5+	1-5														
1+	6-15														
2+	16-25														
3+	26-50														
4+	>50														
[...]															

106/108	
13.4 Appendix 4
 
Eye Pain- Visual Analogue Scale (VAS)
 
Please assess the eye pain by ticking the scale, which describes eye pain the best.
 
  
	89/90	
13.4 Appendix 4
 
Eye Pain/Discomfort - Visual Analogue Scale (VAS)
 
Please assess the eye pain/discomfort by ticking the scale, which describes eye pain/discomfort the best.
 
  
										
107/108	
13.5 Appendix 5
 
Discomfort Assessment
 
Please assess the severity of the eye discomfort by using the following scale.
 
 
  
 Grade	Description	
   
 0	None	
 
 1	Mild	
 
 2	Moderate	
 
 3	Severe	
  
 
	Grade	Description	0	None	1	Mild	2	Moderate	3	Severe	n/a	
There is no previous information about Discomfort Assessment in the protocol version final 1.0 06 November 2019.

Grade	Description												
0	None												
1	Mild												
2	Moderate												
3	Severe												

108/108	13.6 Appendix 6  Photophobia - Visual Analogue Scale (VAS)  [...]		There is no Appendix 6 in protocol version 1.0 06 Nov 2019.
---------	---	--	---

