## 6.7 Prior and Concomitant Medications

All medications (including OTC, vitamins, and antacids) taken 2 months prior to Screening visit (Visit -1) (36 months prior for ocular implants and/or intravitreal injections) and throughout the study duration, must be recorded on the eCRF. The generic name of the drug, dose, route of administration, duration of treatment (including start and stop dates), frequency, indication, and whether or not the medication was taken due to an AE will be recorded for each medication.

Patients will be asked to phone the study center at any time to speak to a member of the medical personnel should they require any concomitant medication.

Medication, which is considered necessary for the patient safety and well-being, may be given at the discretion of the investigator. However, concomitant medication administered during the study may lead to withdrawal of the patient from the IMP (Section [6.7.1](#)).

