### 6.7.1 Prohibited Concomitant Medications

The use of the following medications is not permitted during the study:

- Any systemic or local therapy with corticosteroids (other than the study drug) or immunosuppressant (except pre-surgical and/or surgical administration of 1 drop of a topical NSAID or corticosteroid, at the investigator discretion)
- Any topical ocular medication (except preservative-free antibiotics for prophylactic purposes and preservative-free artificial tears).
- Any systemic NSAID or opioids drugs (except occasional use of OTC formulations titrated no more than one single dose per week)

The aforementioned medications will be considered as rescue medications when administered in patients not responding to the IMP (Section [6.7.2](#)).

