### 6.7.2 Rescue Medication

Any patients not responding adequately to the IMP may be rescued and placed on alternate therapy (Section [6.7](#)) at the investigator's discretion at any time.

The choice of rescue medication is at the investigator's discretion. Any patient placed on rescue therapy will discontinue the use of the IMP and the investigator must make extensive efforts to ensure that the patient will attend all his/her remaining study visits until study completion, aiming to collect the most complete efficacy and safety data.

Additionally, patients will be asked to phone the study center at any time to speak to a member of the medical personnel should they experience any worsening of ocular conditions or other AEs.

Rescued patients will be considered treatment failures, but the need for rescue therapy will not be considered an AE.

---

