### **9.1.11 Key Secondary Analysis**

The aim of the key secondary analysis of this study is to assess the superiority of clobetasol propionate ophthalmic nanoemulsion 0.05% compared to placebo with respect to the key secondary endpoint in the FAS.

The key secondary analysis will be based on a single study eye for each patient. Each patient's study eye will be defined as the surgery eye.

The test will be the proportion of study eyes with no pain (pain = 0) at Visit 3 (Day 8 ± 1 day) without receiving rescue medication as compared between clobetasol propionate ophthalmic nanoemulsion 0.05% dosed QID and placebo dosed QID using the chi square statistic.

The PP population set will be also tested to confirm the robustness of the key secondary analysis.

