### **6.3.6 Secondary Efficacy Analyses**

#### **6.3.6.1 Key Secondary Efficacy Analysis**

The key secondary efficacy endpoint is the proportion of patients with VAS pain score of "0" (no eye pain) compared to placebo at Day 8.

The key secondary analysis will be based on a single study eye for each patient. Each patient's study eye will be defined as the surgery eye.

A Chi-Square test will be performed to test the proportion of study eyes with no pain (VAS = 0) at Visit 3 (Day 8 ± 1 day) without receiving rescue medication as compared between clobetasol propionate ophthalmic nanoemulsion 0.05% dosed QID and placebo dosed QID. The proportion of eyes with no pain together with its 95% confidence interval (CI) will be presented.

Analysis will be conducted both in FAS and PP to test the robustness of the results.

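### A pain-free eye rescued for inflammation fails the key secondary pain test, so unequal rescue can contribute to a significant pain result; SAP 5 contradicts this scoring and no listed output separates the causes of failure

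*Protocol*

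**What the plan says.** Protocol 9.1.11 defines success in the key secondary test as "no pain (pain = 0) at Visit 3 (Day 8 ± 1 day) without receiving rescue medication", and SAP 6.3.6.1 as "no pain (VAS = 0) at Visit 3 (Day 8 ± 1 day) without receiving rescue medication". The new-text column of the Summary of Changes words it as "study eyes with no pain (VAS pain = 0) at Visit 3 (Day 8 ± 1 day) without receiving rescue medication"; the two sections above are the operative text and carry the same rule.

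Protocol 6.7.2 describes the trigger: "Any patients not responding adequately to the IMP may be rescued and placed on alternate therapy", at the investigator's discretion. It adds: "Rescued patients will be considered treatment failures, but the need for rescue therapy will not be considered an AE". Under Protocol 6.7.1 the listed prohibited drugs "will be considered as rescue medications when administered in patients not responding to the IMP". None of this ties rescue to pain.

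The endpoint itself (Protocol 7.2, SAP 3.2) is VAS pain of 0 at Day 8, with no rescue condition. The objective (Protocol 3.2) is an effect on eye pain.

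SAP 5 states a different rule. FAS efficacy analyses use only visits on study treatment with no rescue or prohibited medication, and SAP 6.6 plans no imputation. The per-protocol analysis at Visit 3 removes patients rescued before that visit.

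The only sensitivity table listed, 14.2.19, concerns anterior chamber cells. Table 14.3.10.3 tabulates rescue by drug class and name, not by reason.

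**The concern.** For the cell endpoint, counting rescue as failure fits what is being measured. For pain it can mix two constructs. Entry requires anterior chamber cells but no pain, so a patient can be inflamed and pain-free. If that patient is rescued, the test records a pain failure although VAS may have been 0 throughout. A drug that reduces inflammation should reduce such rescue, and the pain comparison then moves in its favour without any effect on pain.

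The planned indication names inflammation and pain, so the key secondary result will be read as separate evidence on pain. The planned tables would not show how much of a difference came from VAS scores and how much from rescue. The two rules for rescued eyes also give different denominators: scored as failures under SAP 6.3.6.1, left out under SAP 5.

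**Working it through.** **The plan's own figure.** Protocol 9.1.1 sizes the trial on cell clearance: 0.22 versus 0.07, two-sided 0.05, 2:1, 202 evaluable. The odds ratio is (0.22/0.78)/(0.07/0.93) = 3.747, as stated. Pooled-variance power at 202 is 80.2%, so the stated 80% reproduces. No rate or power is given for the pain endpoint, and no rescue rate is given anywhere.

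**Inputs.**
- 140 clobetasol and 70 placebo patients; uncorrected Pearson chi-square, two-sided 0.05 (Protocol 9.1, 9.1.1 and 9.1.11).
- Pain-free rate π, equal in both arms, so there is no true pain effect. Protocol 2.1 reports 55% with no pain or discomfort after this surgery. Adding its 32% with slight discomfort gives 87%, an upper bound because it treats slight discomfort as VAS pain of 0. Neither is a Day 8 rate. 70% is used as a middle value.
- Rescue rate r before Visit 3: assumed, and taken as independent of pain.

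**Formula.** Success rate per arm = π(1 − r). The spurious difference is π(r placebo − r clobetasol). At 5% versus 20% it is 0.55 × 0.15 = 8.3 points up to 0.87 × 0.15 = 13.1 points.

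**Chance of a significant result favouring clobetasol** (exact enumeration of all outcomes):

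| Rescue, clobetasol vs placebo | π = 55% | π = 70% | π = 87% |
|---|---|---|---|
| none | 2.6% | 2.6% | 2.7% |
| 7.8% vs 9.3% | 3.1% | 3.6% | 4.6% |
| 19.5% vs 23.25% | 4.8% | 5.6% | 7.2% |
| 5% vs 10% | 5.5% | 7.4% | 12.4% |
| 5% vs 20% | 19.6% | 32.0% | 58.3% |

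The second and third rows take the plan's expected uncleared eyes at Day 8 (1 − 0.22 = 78% and 1 − 0.07 = 93%) and rescue the same share in each arm: 0.10 × 78% = 7.8% and 0.10 × 93% = 9.3%; 0.25 × 78% = 19.5% and 0.25 × 93% = 23.25%. The last two rows are assumed gaps with no source in the documents.

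**If rescue falls mainly on painful eyes.** Those eyes already fail on VAS, so only rescue among pain-free eyes matters. Suppose rescue of pain-free eyes is half the last row, 2.5% versus 10%. Success becomes π × 0.975 and π × 0.90, and the chance falls to 7.9%, 11.7% and 22.6%.

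**Under the SAP 5 rule.** If rescued eyes are dropped and rescue is independent of pain, simulation (200,000 runs; 5% vs 30% and 10% vs 30% rescue; π = 40%, 55% and 70%) gives two-sided rejection of 5.0% to 5.1%. The inflation arises only under the failure rule.

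**The case against.** Counting rescued patients as failures is a legitimate composite, and the primary analysis uses it too. Rescue drugs can include corticosteroids, systemic NSAIDs and opioids, so VAS 0 after rescue cannot be credited to the assigned arm.

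The 78% and 93% describe eyes with any residual cell, including grade 0.5+. They are not rescue rates, and residual cells are not a stated trigger for rescue. VAS is recorded before any physical evaluation, so cells found at Visit 3 cannot have prompted rescue before that score. Only one scheduled slit-lamp examination, at Visit 2, lies between Baseline and Visit 3. The protocol also links severe pain to inflammation, so rescued eyes may well be painful.

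There are partial checks: the per-protocol pain test removes rescued patients, VAS pain is modelled over visits and diaries, and VAS and rescue are both listed by patient.

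All of this stands as a limit on the size and as a reason to keep the composite. It does not close the gap. The per-protocol test conditions on a post-randomization event and never uses the rescued patients' scores. The VAS models do not address the responder endpoint and fall under the same SAP 5 filter. The general promise of sensitivity analyses is attached to the primary estimand, and no pain table is listed.

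**Conclusion.** The concern holds as a problem of interpretation and consistency. Under Protocol 9.1.11 and 6.7.2 and SAP 6.3.6.1, inflammation-driven rescue of pain-free eyes counts against pain, and an arm difference in it can contribute to a significant pain result. SAP 5 contradicts that scoring.

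The size is not known. With no true pain effect, the false-win chance runs from about 3% to 7% (equal 10% to 25% shares of uncleared eyes rescued), through 5% to 12% (5% vs 10%), to 20% to 58% (5% vs 20%), across pain-free rates of 55% to 87%. These figures assume that rescue is independent of pain, and they fall if rescued eyes are mostly painful.

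A reader might infer three stronger things: that rescue will often occur in pain-free eyes, that a significant result could not be read as a pain effect at all, or that the plan unambiguously fails every rescued eye. The documents support none of these. They give no rescue rates, they link severe pain to inflammation, and SAP 5 states a competing rule. The change is worth making before unmasking, but the key secondary test need not be replaced.

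**What to change.** 1. In SAP 5, state that the visit filter does not apply to the key secondary test, so that rescued patients stay in the FAS denominator as failures, in line with SAP 6.3.6.1 and Protocol 6.7.2. Keep the composite as the key secondary test.
2. In Table 14.2.2.1, split failures by arm into: VAS > 0 without rescue; rescue with VAS = 0 at Visit 3, by recorded indication; rescue with VAS > 0; and missing VAS. Classify indications while masked, for example at the blind data review meeting, with a written rule for unclear entries.
3. Add one supportive FAS analysis, also exempt from the filter. Patients rescued for inflammation only are classified by their observed Visit 3 VAS; VAS > 0, missing VAS, or rescue whose indication includes pain remains a failure. Report the difference with its 95% CI and use it to interpret the composite, not as a gate.

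The cost is SAP wording, a matching note in Protocol 9.1.11 and one extra table. The data are already planned: under Protocol 6.7 the "frequency, indication, and whether or not the medication was taken due to an AE will be recorded for each medication", and rescued patients are asked to attend all remaining visits. The downside is that VAS after rescue may be lowered by the rescue drug, so the supportive analysis may understate a real pain effect. Who is rescued, and with what, does not change.
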